6.1.6 Completion of the study

Patients will receive study treatment for a maximum of two years or until disease progression. The study will be completed if progression of liver metastases is confirmed by the follow-up imaging studies. Patients will also be removed if they develop progression of extra-hepatic metastases for two consecutive imaging studies unless palliative radiation or surgical resection of progressive disease is feasible. Patients will be removed if they develop an unacceptable serious adverse event. If they fail to fulfill the eligibility criteria for the combination treatment, the patient will also be removed from the study.

At the time of study completion, the following studies and procedures will be performed:

- 1. Medical history to include determination of tumor-related symptoms
- 2. Physical examination to include ECOG performance status, weight, and vital signs
- 3. CT of the chest (with contrast), CT of abdomen and pelvis (with and without contrast), and MRI of the abdomen (with and without contrast)...if they are not ordered within 4 weeks of completion of the study
- 4. Blood draw for tests to include the following:
 Routine: complete blood count (CBC) with differential white blood count, serum laboratory studies including total bilirubin, SGOT, SGPT, LDH, alkaline phosphatase, albumin, TSH, creatinine, BUN, glucose, calcium, and phosphorus; Research: biomarker testing (60 ml) and immunological testing (10 ml).

6.1.7 Follow-up after study completion

All patients, including patients who discontinue protocol therapy because of toxicity or progressive disease must be followed every three months up to a minimum of 1 year to determine clinical status and to document time to progression and duration of survival. Telephone contact is allowed for this purpose.

6.2 Adverse Events and Potential Risks

Please see appendix 16.2 detailing potential adverse drug events (ADRs) that may be attributable to ipilimumab and nivolumab combination or nivolumab alone. In general side effects related to ipilimumab and nivolumab are considered immune related adverse events and include but are not limited to dermatitis, hepatitis, pneumonitis, colitis, endocrinopathy (including hypophysitis and thyroiditis), and nephritis. Appendix tables adopted from Investigator Brochure addendum.

6.3 Dose Delays and Dose Modifications

6.3.1 Attributed to Immunoembolization with GM-CSF

If CTC Grade 4 systemic and or local toxicities related to GM-CSF are observed, no further dose will be offered, with the exception of Grade 4 AST/ALT elevation as long as resolves within 7 days.

6.3.2 Attributed to Ipilimumab, Ipilimumab or Nivolumab, or Nivolumab alone. See Appendix 3 for management of immune related toxicities.

6.3.3 Attributed to combination of Ipilimumab and Nivolumab and Immunoembolization or Nivolumab and Immunoembolization

Combination treatment could be postponed for up to 10 weeks (from the date of next scheduled treatment). if patients need a treatment break for immune related toxicity. During combination treatment with IPI and NIVO, depending on type and severity of toxicity, patient may be able move onto the maintenance phase of NIVO + IEMBO and drop the IPI before the full four combination doses are given. Likewise, NIVO may also be dropped and patient may be able to continue on with IEMBO only, if the investigator feels patient is receiving clinical benefit from it. These determinations may be made at the investigator's discretion, in consideration of patient safety.

A window of +/- 3 days is permitted between each treatment cycle beginning at cycle 2 and will not be characterized as dose or treatment delay.

7.0 STATISTICAL PLAN

7.1 Sample Size Determination

The trial will enroll 13 patients in the first stage. If there are 8 or fewer responses in these 13 patients, the study will be stopped. If the trial goes on to the second stage, 22 additional patients will be accrued for a total of 35 patients. The sample sizes for each stage are computed for optimal minimax design to test the null hypothesis that hepatic metastasis stabilization rate \leq 60% versus the alternative that stabilization rate \geq 80% using one-sided test with a target a type I error rate of 0.05.

7.2 Statistical Methods

The trial is designed with the potential for early termination in the case of a poor hepatic metastasis stabilization rate (hepatic response). The design will be a two-stage optimal minimax design using the method of Simon, augmented with admissible choices. Choice of design is guided by a desire to stop the trial early if the actual metastasis stabilization rate is 60% (as experienced with IEMBO alone) or less. If the metastasis stabilization rate is 80% or greater, we would like to have a low probability of failing to conclude that IEMBO + IPI + NIVO is effective. The trial will enroll 13 patients in the first stage. If in these 13 patients, 8 or fewer patients have hepatic metastasis stabilizations, the study will be stopped. If the trial goes on to the second stage, 22 additional patients will be accrued for a total of 35 patients. The combination IEMBO + IPI + NIVO will be considered ineffective if there are 25 or fewer responses (hepatic metastasis stabilizations) in 35 patients. With this design, we have no more than a 19% chance of concluding that combination IEMBO + IPI + NIVO is ineffective (≤60% success rate) when the success rate is at least 80%. Similarly, we have no more than a 5% chance of concluding effective (≥60% success rate) when it is ineffective. If the actual metastasis stabilizations rate is 60% or worse, we have at least a 0.65 probability that the trial will stop after the first 13 subjects.

7.2.1 Analysis Population

The evaluable population includes all subjects enrolled who receive at least four combination treatments (IPI + NIVO + IEMBO at initial every 3 week intervals or NIVO + IEMBO if IPI dropped due to toxicity and IEMBO alone if NIVO dropped due to toxicity) and complete assessment after four treatments.

The As-treated population includes all subjects who receive any treatment and will be used to evaluate baseline characteristics as well as all secondary endpoints for safety and efficacy as the collected data allows.

7.2.2 Primary Endpoint:

The primary endpoint is the best hepatic response (CR + PR + SD) by response criteria (RECIST 1.1) after four combination treatments. The estimate of the hepatic metastasis stabilization rate will be presented with corresponding 95% confidence intervals. The method of Atkinson and Brown will be used to adjust for the two-stage design.

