4.3 Early Withdrawal of Subjects

4.3.1 When to Withdraw Subjects

An individual subject will not receive any further investigational product if any of the following occur in the subject in question:

- 1. Withdraw of consent or lost to follow up.
- 2. Subject is determined to have met one or more of the exclusion criteria and continuing therapy may be a safety risk
- 3. Pregnancy or intent to become pregnant
- 4. Any adverse event that meets criteria for discontinuation
- 5. Subject non-compliance that in the opinion of the investigator or sponsor warrants withdrawal
- 6. Initiation of alternative anti-cancer therapy
- 7. Confirmation of progression of disease

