4.3.3 Replacement of Subjects

Should a subject be withdrawn from the study prior to the assessment at the fourth cycle for any other reason besides clinical deterioration or toxicity they will be replaced as they will not be evaluable.

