5.4 Treatment Regimen Combination

Patients will be seen in the outpatient office on Day #1 of every cycle and receive administration of ipilimumab and nivolumab or once in maintenance phase nivolumab alone. On Day #2 they will undergo IEMBO consisting of intra hepatic artery administration of GM-CSF (1500mcg) mixed with ethiodized oil emulsion, followed by embolization of the hepatic artery with gelatin sponge particles under the care of interventional radiology. Patients will undergo this combination intervention every 3 weeks for 12 weeks unless significant disease progression, limiting toxicity, or withdrawal of consent. Interim imaging after 2 cycles will be peformed to ensure there has not been rapid progression. After four combination treatments if noted to have CR, PR, or SD patients will be offered maintenance therapy with combination intervention every 4 weeks until disease progression, limiting toxicity, or withdrawal of consent. When undergoing every 4 week maintenance patients will receive NIVO on Day #1 and IEMBO on Day #2 of each 28 day cycle.

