6.1.4 Office visit after 4 cycles

After the fourth cycle patients will be evaluated for response. The tests and procedures described below will be performed.

- 1. Medical history to include determination of tumor-related symptoms
- 2. Physical examination to include ECOG performance status, patient height and weight, vital signs
- 3. CT of the chest (with contrast), CT of abdomen and pelvis (with and without contrast), and MRI of the abdomen (with and without contrast)
- 4. Blood tests to include the following

Complete blood count (CBC) with differential white blood count. Serum laboratory studies including total bilirubin, SGOT, SGPT, LDH, alkaline phosphatase, albumin, TSH, creatinine, BUN, glucose, calcium, and phosphorus. Sixty (60) ml of blood will also be drawn for immunological testing.

After the completion of 4 treatments, continuation of the treatment will be offered to patients who have demonstrated clinical benefit from the treatment and have not experienced any CTC grade 4 toxicity while participating in this study. If the patient started with unilobar disease but develops liver metastases in the contralateral lobe treatment to the contralateral lobe with immunoembolization and continuation of the treatment will be allowed.

If patients have progression of liver metastases, or progression of extra-hepatic metastases that require a change in systemic therapy (palliative radiation or surgery allowed as per discretion of investigator) determined by RECIST 1.1, or experienced serious side effects, patients will be removed from the study and appropriate medical advice regarding alterative treatment options will be provided (See Section 6.1.6 Completion of the study).

If patients have unequivocal progression of hepatic metastasis prior to the visit after 4 treatments, they may be removed from the study at the discretion of the investigators and appropriate medical advice will be provided. In that case, patients will be followed every 3 months to document their medical condition until their death. Follow-up over the telephone will be performed for patients unable to return for examination. If there is a mixed response seen at the interim scan completed between cycles 2 and 3, and it is deemed patient is getting clinical benefit, they will be allowed to continue with study treatment.

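### Sections 7.2.1, 4.3.3 and 9.1 define evaluability incompatibly and 7.2.2 names no primary population; the set left by elimination omits early hepatic progressors and early deaths, which biases the reported stabilization rate upward

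*Combined protocol and SAP*

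**What the plan says.** Three sections of the combined protocol and SAP say who is evaluable.

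- **7.2.1:** "The evaluable population includes all subjects enrolled who receive at least four combination treatments" "and complete assessment after four treatments". Treatments still count if ipilimumab or nivolumab was dropped for toxicity.
- **4.3.3:** a patient withdrawn before the fourth-cycle assessment "for any other reason besides clinical deterioration or toxicity they will be replaced as they will not be evaluable". By implication, patients withdrawn for deterioration or toxicity are not replaced and stay evaluable.
- **9.1:** one IEMBO is enough to be evaluable for clinical response; patients who could not have IEMBO for technical reasons are left out.

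Section 7.2.2 names no population for the primary endpoint. The other set in 7.2.1 is reserved: "The As-treated population includes all subjects who receive any treatment and will be used to evaluate baseline characteristics as well as all secondary endpoints". 

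Patients can leave before the post-cycle-4 assessment because their disease progressed. Section 6.1.4 says: "If patients have unequivocal progression of hepatic metastasis prior to the visit after 4 treatments, they may be removed from the study". Section 5.4 plans combination treatment "every 3 weeks for 12 weeks unless significant disease progression, limiting toxicity, or withdrawal of consent". Section 4.3.1 has "Confirmation of progression of disease" as a withdrawal reason of its own.

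The decision rule in 7.1 and 7.2 is in counts: stop at 8 or fewer of 13; ineffective at 25 or fewer of 35.

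**The concern.** The endpoint is absence of progression in the liver. A denominator restricted to patients who complete four treatments and the assessment is conditioned partly on not having failed. A patient taken off study for hepatic progression after the interim scan, or who dies before the assessment, has failed on the endpoint, yet is absent from the 7.2.1 set. Section 9.4 turns unconfirmed stable disease into progression, but gives no rule for a patient with no post-cycle-4 assessment.

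At stake is the trial's single primary estimate. The same data give different rates under the three definitions, and in an open-label, single-arm trial the choice could be made after the data are seen. A second question is whether early failures might be replaced, because that would affect the decision rule as well as the estimate.

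**Working it through.** **1. The definitions applied to the same patients**

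| Patient leaving before the post-cycle-4 assessment | 7.2.1 | 4.3.3 | 9.1 |
|---|---|---|---|
| Two IEMBOs, withdrawn for clinical deterioration | out | in (implied) | in |
| One IEMBO, withdraws consent | out | out, replaced | in |
| Two IEMBOs, radiographic hepatic progression, clinically well | out | not stated | in |

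Each pair of definitions disagrees on at least one of the first two patients.

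**2. The plan's design reproduced**

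Inputs from the Study Summary, 7.1 and 7.2: null 0.60, alternative 0.80, n1 = 13, r1 = 8, n = 35, r = 25. With X1 ~ Bin(13, p) and X2 ~ Bin(22, p):

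- Probability of early termination: PET(p) = P(X1 ≤ 8)
- Probability of declaring efficacy: Σ over x = 9 to 13 of P(X1 = x) · P(X2 ≥ 26 − x)

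At p = 0.60, PET is 0.647 and type I error 0.0499. At p = 0.80, power is 0.808 and type II error 0.192. These agree with the stated 0.65, 5%, 80% and 19% to rounding.

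**3. Effect on the reported rate**

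Leaving out k early failures changes x/35 to x/(35 − k). The values of k are assumed; the intervals are single-stage exact 95%, for illustration.

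| Stabilized | All 35 | k left out | Reported |
|---|---|---|---|
| 25 | 71% (54–85%) | 4 | 25/31 = 81% (62.5–92.5%) |
| 21 | 60% (42–76%) | 5 | 21/30 = 70% (51–85%) |

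In the first row, a result that 7.2 calls ineffective is reported above the 80% target, with a lower limit above the 60% null.

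**4. Effect on the decision rule without replacement**

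Leaving out a failure does not change the number of successes: 25 stays 25, below 26. If 8/13 and 25/35 are counts in a set that keeps early failures and does not replace them, the figures in step 2 stand.

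**5. Conditional: clinically well radiographic progressors are replaced**

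If they are a fraction g of treated patients, the success probability per counted patient at a true 60% is 0.60/(1 − g). The documents give no g; the range is assumed.

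| g | 0.60/(1 − g) | Type I error | PET |
|---|---|---|---|
| 2% | 0.612 | 0.067 | 0.61 |
| 5% | 0.632 | 0.10 | 0.56 |
| 10% | 0.667 | 0.20 | 0.45 |

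**6. Cost of keeping toxicity leavers in the denominator**

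If a fraction L of otherwise stabilized patients leave early and do not meet 9.4, the true rate is 0.80(1 − L). For L = 2.5%, 5% and 10% (assumed), that is 0.78, 0.76 and 0.72, and power is 0.72, 0.63 and 0.42.

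**The case against.** **The go/no-go rule is sound as written.** This stands. A reader might infer from the table in step 5 that the plan's type I error is already inflated. The documents do not support that. The boundaries are counts in 13 and 35 patients, and 4.3.3 bars replacement for clinical deterioration, which could be read to include progression: neither 4.3.1 nor 5.4 lists deterioration as a reason, so progression is its nearest counterpart. Section 6.1.5 does describe RECIST progression without clinical deterioration, so the protocol treats the two as separable, but it does so to let such patients continue treatment. Removal before cycle 4 is discretionary and mixed responders may stay. The gap is real; the inflation is conditional on it and on assumed fractions.

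**Not every exclusion biases upward.** This also stands. The 7.2.1 set drops patients who stop all treatment for toxicity, some with stable livers. The direction is certain only for progression and death.

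**The interval.** A reader might infer that the interval in 7.2.2 fails unless the set has exactly 13 and 35 patients. The text says only that the named method "will be used to adjust for the two-stage design", which does not establish that.

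**Scoring toxicity withdrawals.** A reader might take 4.3.3 to make every toxicity withdrawal a failure. It implies only that they are not replaced; 6.1.6 provides exit scans and 9.4 provides criteria.

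**The 60% benchmark.** Section 1.1 does not give its denominator. If it came from patients who completed treatment, the four-treatment set would be the like-for-like comparison. This cannot be checked from the documents, and is a reason to state the denominator and keep that set as a sensitivity analysis.

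**Conclusion.** The point holds. The three definitions conflict in current text, 7.2.2 names no population, and the four-treatment set is primary only by elimination. Used as written, that set removes early hepatic progressors who are taken off study and early deaths, and this part biases the reported rate upward. The illustrated shift of about 9 points (71% to 81%, unrounded 71.4% to 80.6%) rests on four assumed early failures in 35; the documents give no expected number. Nothing here shows that the decision rule is invalid. Its type I error is exposed only to the extent that 4.3.3 is read to allow replacement of clinically well progressors. The matter should be settled before analysis, because it concerns the only primary result and needs only wording.

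**What to change.** - **7.2.1 and 7.2.2:** name one primary set, all patients who receive any study treatment except those replaced under 4.3.3. Apply 8/13 and 25/35 as counts in it.
- **Scoring:** hepatic progression or death before the post-cycle-4 assessment is not stabilized. Toxicity and deterioration withdrawals stay in the denominator and are scored by the 9.4 criteria, with its confirmation rule, from the interim and exit scans the protocol already obtains; if those scans do not meet the criteria, the patient is not stabilized. Section 9.4 starts response evaluation after four treatments, so say explicitly that earlier scans are used for these patients.
- **4.3.3:** state that progression, including radiographic-only progression, and death are never replaced. List all replaced patients with reasons.
- **9.1:** reconcile with this set, including the exclusion of technical IEMBO failures. Infusions are on Day 1 and IEMBO on Day 2, so such a patient may already have received study treatment.
- **Benchmark:** state the denominator behind the 60%.
- **Sensitivity analyses:** the four-treatment set, and all treated patients with no exclusions.

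The cost is wording in four sections plus the benchmark statement, with no new procedures. The downsides are a lower reported rate and the loss of power in step 6. The power loss is limited because patients who drop ipilimumab or nivolumab but reach four treatments are still assessed, and because leavers with qualifying scans still count as stabilized.

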7.2.3 Secondary and Exploratory (Correlative) Endpoints

- 1. All toxicities using the NCI CTCAE Version4.0.
- 2. PFS (hepatic and systemic PFS)
- 3. Overall survival
- 4. Systemic and local immune/inflammatory response correlatives
 - a. Degree and classification of tumor-infiltrating cells
 - b. Presence and changes in PD-L1 expression in tumor and tumor-infiltrating cells
 - c. Changes in immune tumor microenvironment (immune gene signature)
 - d. Tumor mutational burden prior to treatment
 - e. Changes in TCR repertoire analysis (ImmunoSeq)
 - f. Changes in cytokine levels (multiplex cytokine measurements)
 - g. Changes in PBMC cell populations, including T cells and MDS.

The PFS and OS will be estimated using the Kaplan-Meier method. The toxicity rates will be estimated with corresponding 95% confidence intervals. Correlative endpoints including repeated measures of cytokine and molecular marker levels in tissue or serum will be analyzed using appropriate linear mixed effects models.

8.0 SAFETY AND ADVERSE EVENTS

8.1 Definitions

8.1.1 Adverse Event

An adverse event is any untoward or unfavorable medical occurrence in a human participant, including any abnormal sign (for example, abnormal physical exam or laboratory finding), symptom, or disease, temporally associated with the participant's participation in the research, whether or not considered related to the participant's participation in the research.

An **adverse event** (AE) is any symptom, sign, illness or experience that develops or worsens in severity during the course of the study. Intercurrent illnesses or injuries should be regarded as adverse events. Abnormal results of diagnostic procedures are considered to be adverse events if the abnormality:

- results in study withdrawal
- is associated with a serious adverse event
- is associated with clinical signs or symptoms
- leads to additional treatment or to further diagnostic tests
- is considered by the investigator to be of clinical significance

8.1.2 Serious Adverse Event

A serious adverse event (SAE) is one that meets one or more of the following criteria:

- Results in death
- Is life-threatening (places the participant at immediate risk of death from the event as it occurred)
- Is disabling or incapacitating
- Results in inpatient hospitalization or prolongation of existing hospitalization
- Results in a persistent or significant disability or incapacity
- Results in a congenital anomaly or birth defect
- An important medical event that may not result in death, be life threatening, or require hospitalization may be considered an SAE when, based upon appropriate medical judgment, the event may jeopardize the participant or may require intervention to prevent one of the outcomes listed in this definition.

Adverse events are classified as serious or non-serious.

A **serious adverse event** is any AE that is:

fatal

- life-threatening
- requires or prolongs hospital stay
- results in persistent or significant disability or incapacity
- a congenital anomaly or birth defect
- an important medical event

Important medical events are those that may not be immediately life threatening, but are clearly of major clinical significance. They may jeopardize the subject, and may require intervention to prevent one of the other serious outcomes noted above. For example, drug overdose or abuse, a seizure that did not result in in-patient hospitalization, or intensive treatment of bronchospasm in an emergency department would typically be considered serious.

All adverse events that do not meet any of the criteria for serious should be regarded as **non-serious adverse events**.

